3.5. Missing Data and Outliers

3.5.1. Missing Data

In general, missing data will not be imputed unless methods for handling missing data are specified.

For missing last dosing date of study drug, imputation rules are described in Section 3.7.1. The handling of missing or incomplete dates for adverse event (AE) onset is described in Section 7.1.5.2, and for prior and concomitant medications in Section 7.8.

For analyses of categorical HCV RNA data, missing posttreatment HCV RNA data will have the missing data imputed. Missing on-treatment HCV RNA will have the missing data imputed up to the time of the last dose (for on-treatment displays). If the study day associated with the last dosing date is greater than or equal to the lower bound of a visit window, and the value at the visit is missing, the value will be imputed. If the study day associated with the last dosing date is less than the lower bound of a visit window, then the on-treatment value at that visit will remain missing.

If a data point is missing and is preceded and followed in time by values that are “< lower limit of quantitation (LLOQ) target not detected (TND)”, then the missing data point will be set to “< LLOQ TND”. If a data point is missing and preceded and followed by values that are “< LLOQ detected”, or preceded by “< LLOQ detected” and followed by “< LLOQ TND”, or preceded by “< LLOQ TND” and followed by “< LLOQ detected”, then the missing value will be set to “< LLOQ detected”. In these situations, the data point will be termed a bracketed success; otherwise, the data point will be termed a bracketed failure (ie, \geq LLOQ detected). If a data point is missing and is not bracketed, the missing data point will also be termed a failure (ie, \geq LLOQ detected) except for SVR24, which will be imputed according to SVR12 status. Success for SVR12 who have no further HCV RNA measurements collected will be counted as a success for SVR24 due to the high correlation between these 2 endpoints.

For the analyses of continuous HCV RNA efficacy data, when and only when a missing HCV RNA value is imputed as < LLOQ TND or < LLOQ detected according to the imputation rule described above, the corresponding continuous value will be imputed to LLOQ - 1 IU/mL. No other imputation will be performed for continuous HCV RNA data.

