3.7.2. Analysis Windows

Subject visits might not occur on protocol-specified days. Therefore, for the purpose of analysis, observations will be assigned to analysis windows.

In general, the baseline value will be the last nonmissing value on or prior to the first dose date of study drug.

HCV RNA, vital signs, and safety laboratory data collected up to the last dose date + 3 days are considered to be on-treatment data and HCV RNA, vital signs and safety laboratory data collected after the last dose date + 3 days are considered posttreatment data. Given the fact that only DAA-naïve subjects without cirrhosis have been enrolled in this study, the analysis windows for on-treatment HCV RNA, vital signs and safety laboratory data are provided in [Table 3-1](#).

Table 3-1. Analysis Windows for On-treatment HCV RNA, Vital Signs and Safety Laboratory Data

Nominal Visit	SOF/VEL/VOX 8 Weeks		
	Nominal Day	Lower Limit	Upper Limit
Baseline	1	(none)	1
Week 1	7	2	11
Week 2	14	12	21
Week 4	28	22	42
Week 8	56	43	≥ 57

HCV RNA, vital sign, and safety laboratory data collected after the last dose date + 3 days will be assigned to the posttreatment follow-up (FU) visits. Visit windows will be calculated from the last dose date (ie, FU Day = collection date minus the last dose date) as shown in [Table 3-2](#).

Table 3-2. Analysis Windows for Posttreatment HCV RNA, Body Weight, Height, Vital Sign and Safety Laboratory Data

Nominal FU ^a Visit	HCV RNA, Body weight and Height			Vital Signs and Safety Laboratory Data ^b		
	Nominal FU Day	Lower Limit	Upper Limit	Nominal FU Day	Lower Limit	Upper Limit
FU 4	28	21	69	28	4	30
FU 12	84	70	146	NA	NA	NA
FU 24	168	147	210	NA	NA	NA

a FU x visit = posttreatment Week x follow up visit.

b Vital signs (blood pressure, pulse, respiratory rate, and temperature) and safety labs will only be summarized for the FU 4 visit (up to 30 days after last dose).

3.7.3. Selection of Data in the Event of Multiple Records in an Analysis Window

Depending on the statistical analysis method, single values may be required for each analysis window. For example, change from baseline by visit usually requires a single value, whereas a time-to-event analysis would not require 1 value per analysis window.

If multiple valid nonmissing numeric observations exist in an analysis window, records will be chosen based on the following rules if a single value is needed:

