4. SUBJECT DISPOSITION

4.1. Subject Enrollment and Disposition

A summary of subject enrollment will be provided for each country, investigator within a country, and overall. The summary will present the number and percentage of subjects in the Safety Analysis Set. For each column, the denominator for the percentage calculation will be the total number of subjects analyzed for that column.

A summary of subject disposition will be provided. This summary will present the number of subjects screened, enrolled, enrolled but never treated, and the number and percentage of subjects in each of the categories listed below. For the “Treated” category, the denominator for the percentage calculation will be the total number of subjects enrolled. For all other categories, the denominator for the percentage calculation will be the total number of subjects in the Safety Analysis Set.

- Treated (Safety Analysis Set)
- In FAS
- In Intensive PK Analysis Set
- In Population PK Analysis Set
- Completed study treatment
- Did not complete study treatment with reasons for premature discontinuation of study treatment
- Completed the study
- Did not complete the study with reason for premature discontinuation of study

Among subjects who completed the study treatment and who discontinued study treatment, the following number and percentage of subjects will be summarized:

- Subjects who had no HCV posttreatment Week 4 assessment and thereafter (No HCV FU-4 and thereafter)
- Subjects who had HCV posttreatment Week 4 assessment but no HCV posttreatment Week 12 assessment and thereafter (With HCV FU-4 but no FU-12 and thereafter)

If a subject did not have any HCV RNA assessment ≥ 21 days after the last dose of any study drug (ie, lower bound of FU-4 visit for HCV RNA data), the subject is categorized as having “No HCV FU-4 and thereafter”. If a subject had the HCV FU-4 assessment but did not have any

HCV RNA assessment ≥ 70 days after the last dose of any study drug (ie, lower bound of FU-12 visit for HCV RNA data), the subject is categorized as having “With HCV FU-4 but No FU-12 and thereafter”.

In addition, the total number of subjects who were enrolled, and the number of subjects in each of the disposition categories listed above will be displayed in a flowchart.

The following by-subject listings will be provided by subject ID number in ascending order to support the above summary tables:

- Disposition of subjects who complete study treatment and study

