6.2.2. Analysis Methods for Secondary Efficacy Endpoints

For analyses of HCV RNA $<$ LLOQ by visit while on treatment and during the posttreatment (SVR) follow-up period, subjects will be assigned a value at each visit based on the analysis visit windows specified in Section 3.7.2. Missing values will be imputed based on the categorical imputation rules described in Section 3.5.1. The 2-sided 95% exact confidence interval based on Clopper-Pearson method will be provided for the percentage of subjects with HCV RNA $<$ LLOQ at each visit. The overall category for “HCV RNA $<$ LLOQ” will be split into the following 2 subcategories: “ $<$ LLOQ TND” for subjects with target not detected and “ $<$ LLOQ detected” for subjects with $<$ LLOQ detected in tabular displays.

Graphs for the percentage of subjects with HCV RNA $<$ LLOQ over time during treatment will be displayed.

Summary statistics will be presented for absolute values and change from baseline in HCV RNA (\log_{10} IU/mL) by visit through EOT. Imputation rules described in Section 3.5.1 will be used to assign HCV RNA values for missing values at a visit that are bracketed by “ $<$ LLOQ TND” and/or “ $<$ LLOQ detected”. Otherwise, a missing excluded analysis will be performed. Plots of the mean \pm SD and median (Q1, Q3) of absolute values and changes from baseline in HCV RNA through EOT will be presented.

For the SVR12 endpoint analysis, a summary table of the number and percentage of subjects with SVR12, virologic failure (VF), and Other will be created by HCV genotype (1 [further broken down to 1a and 1b], 2, 3, 4, 5, 6, or other, as appropriate, and total). All subjects who achieve SVR12 will be categorized as SVR12. Virologic failure will be descriptively summarized as “on-treatment virologic failure” and relapse (which will be broken down by study drug completed yes/no). Subjects who do not achieve SVR12 and do not meet criteria for VF will be categorized as Other. The denominator for relapse will be the number of subjects who had HCV RNA < LLOQ on their last observed on-treatment HCV RNA measurement; otherwise, the denominator will be the number of subjects in the FAS.

A concordance table between SVR12 and SVR24 will be provided. Subjects with both observed SVR12 and observed SVR24 data will be included for this analysis.

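### SAP 3.7.2 gives HCV RNA on FU Days 4-20 no analysis window, so an observed end-of-treatment result can be displaced by an imputed one and ignored in the relapse denominator

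*SAP*

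**What the plan says.** SAP 3.7.2 sets the boundary between periods: HCV RNA, vital signs and "safety laboratory data collected up to the last dose date + 3 days are considered to be on-treatment data". Beyond that boundary, the same three data types go to follow-up visits ("safety laboratory data collected after the last dose date + 3 days will be assigned to the posttreatment follow-up (FU) visits"), with windows read from Table 3-2 and time counted as "FU Day = collection date minus the last dose date".

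In Table 3-2 the FU 4 row has nominal day 28 in both halves. The window is FU Days 21-69 for HCV RNA, weight and height, and FU Days 4-30 for vital signs and laboratory data. SAP 4.1 repeats 21 days as the "lower bound of FU-4 visit for HCV RNA data".

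Three other rules depend on these windows:

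- SAP 3.5.1 imputes a missing on-treatment categorical value when the last dosing day has reached the lower bound of the visit window. The imputed value is below LLOQ only if the values before and after are both below LLOQ. "If a data point is missing and is not bracketed, the missing data point will also be termed a failure", with an exception for SVR24 only.
- SAP 6.2.2 assigns by-visit HCV RNA through the windows of 3.7.2, and restricts the relapse denominator to subjects below LLOQ "on their last observed on-treatment HCV RNA measurement".
- SAP 6.2.1 defines relapse as a posttreatment value at or above LLOQ after a value below LLOQ at end of treatment. It does not say which sample represents end of treatment.

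**The concern.** Read literally, 3.7.2 sends every HCV RNA result after last dose + 3 days to a follow-up visit, but for 17 days there is no visit to receive it. The samples most likely to fall there are those meant to show viral status when dosing stops. Protocol 6.3.5 requires HCV RNA at End of Treatment or Early Termination and gives no interval from last dose for the latter.

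If such a sample has no window, the window containing the last dose is empty and is imputed. A subject seen to be suppressed shortly after stopping could then be displayed as at or above LLOQ. The relapse denominator would rest on an earlier result. The choice would also be left to the programmer, in an open-label study with few subjects.

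**Working it through.** **1. The gap.** Inputs from SAP 3.7.2: on-treatment means FU Day ≤ 3, and the first HCV RNA follow-up window starts at FU Day 21. The SAP's own figure of 21 agrees between Table 3-2 and SAP 4.1, so it is not a misprint. Unassigned days run from 4 to 20: 20 − 4 + 1 = 17. Applying the rules to every FU Day from 1 to 210 leaves exactly these 17 without a window. Laboratory data have no gap over FU Days 1-30, because their window starts at FU Day 4. The open upper limit of the Week 8 window in Table 3-1 does not rescue the record, because the + 3 days rule has already made it posttreatment.

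**2. Can a sample land there?** Early Termination: yes, whenever the visit is 4 to 20 days after the last tablet. End of Treatment, taking Week 8 as Day 56 (Table 3-1) with the protocol's ±3 days, may be on Days 53-59:

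| Last dose | Last on-treatment day (dose + 3) | Permitted visit days with no window |
|---|---|---|
| Day 53 | 56 | 57, 58, 59 |
| Day 54 | 57 | 58, 59 |
| Day 55 | 58 | 59 |
| Day 56 | 59 | none |

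**3. What is imputed?** Suppose the last dose is on or after the lower bound of the window (Day 22 for Week 4, Day 43 for Week 8) and the only sample for that visit is on FU Days 4-20 and below LLOQ. SAP 3.5.1 speaks of values before and after in time. It does not say whether a record with no window may be one of them, so both readings are shown:

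| Preceding on-treatment value | Next windowed follow-up value | Only windowed values bracket | Any value in time brackets |
|---|---|---|---|
| ≥ LLOQ | any or none | failure | failure |
| < LLOQ | < LLOQ | success | success |
| < LLOQ | ≥ LLOQ | failure | success |
| < LLOQ | none | failure | success |

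The first row gives a failure on either reading, against an observed suppressed result.

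**4. Relapse.** Example: last dose Day 24; Week 2 HCV RNA 40 IU/mL (LLOQ is 15); Early Termination sample on Day 29 below LLOQ; high HCV RNA at FU-4.

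- FU Day = 29 − 24 = 5, so the sample has no window, although Day 29 lies inside the Week 4 study-day range of 22-42.
- Day 24 is past the Week 4 lower bound of 22, so Week 4 is imputed. The preceding value is 40, so the result is at or above LLOQ.
- The last observed on-treatment value is 40, so the subject is outside the relapse denominator.
- No on-treatment failure definition is met: no on-treatment value below LLOQ (breakthrough), no rise from nadir on treatment (rebound), and no 8 weeks of treatment (nonresponse).
- If the Early Termination sample counts as end of treatment, the subject is a relapse under 6.2.1 and is in the numerator without being in the denominator.

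**5. Size of one case.** Assume n = 20, the planned cohort minimum. One subject is 1/20 = 5 percentage points. If one subject is wrongly imputed as a failure at Week 8, the proportion below LLOQ moves from 20/20 (Clopper-Pearson 95% CI 83.2%-100%) to 19/20 = 95% (75.1%-99.9%).

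**The case against.** The strongest reply is that the Day 21 limit is deliberate. It is stated twice and protects SVR4 from samples taken too soon after treatment. On this view the assignment sentence simply points to Table 3-2 and does not promise every record a window. Laboratory data after FU Day 30 also have none, and a footnote says so. That stands as a defence of the limit. It does not supply a rule for FU Days 4-20, and no footnote covers that interval for HCV RNA.

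The second reply is that harm is uncommon. A subject with Week 4 and FU-4 both below LLOQ is imputed as a success. If any value in time may bracket, so is every subject whose preceding value was below LLOQ. That also stands. A reader might infer that a suppressed sample in the gap is generally turned into a failure; the documents support this only where the preceding value is at or above LLOQ or no usable bracketing value exists.

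Third, a reader might infer that the subject in the example must be classed as Other. This is not forced. The relapse definition in 6.2.1 is not tied to windows, and the protocol treats End of Treatment and Early Termination as one visit section, so the sample can qualify. What remains is the mismatch between numerator and denominator.

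Finally, the example needs several conditions at once, and a last dose on Day 56 followed by a visit by Day 59 is safe. That bears on frequency, not on whether the rules conflict.

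**Conclusion.** The point holds as a minor defect in the analysis rules. SAP 3.7.2 leaves 17 days without an HCV RNA window. In the circumstances set out above, following 3.5.1 and 6.2.2 as written displays an imputed failure over an observed result below LLOQ and bases the relapse denominator on an older value.

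A reader might extend this to the main results, but the documents do not support that. The primary endpoint is PK. SVR12 uses FU Days 70-146 and is not directly affected. SAP 6.1.2 plans no inferential efficacy statistics, and the record remains in the by-subject listings. The exposed outputs are descriptive: HCV RNA below LLOQ at the last on-treatment visit, HCV RNA change through end of treatment, and the relapse proportion.

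The documents do not give the number of subjects affected. Assuming 0 to 2 of about 20, the effect is 0 to 10 percentage points at the visit concerned, at 5 points each, if every one were imputed as a failure.

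**What to change.** - **SAP 3.7.2 and 3.5.1:** state that, if no HCV RNA exists in the on-treatment window containing the last dose, the End of Treatment or Early Termination HCV RNA from FU Days 4-20 is used in the by-visit display whatever its result, flagged as off drug, in place of imputation. State also that it may serve as a bracketing value. The record stays posttreatment for the on-treatment failure definitions. The rule should not depend on the result: counting only values below LLOQ as end-of-treatment values could only raise the displayed suppression rate.
- **SAP 6.2.1 and 6.2.2:** define end of treatment for relapse identically in numerator and denominator, as a last on-treatment value below LLOQ or an End of Treatment or Early Termination value below LLOQ.
- **Table 3-2:** leave the FU-4 lower limit of Day 21 for SVR4 as it is.

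The cost is a few sentences in the SAP and a small change to the window derivation. The drawback is that a few displayed end-of-treatment values may be up to 20 days off drug, which the flag makes visible.

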4. SUBJECT DISPOSITION

4.1. Subject Enrollment and Disposition

A summary of subject enrollment will be provided for each country, investigator within a country, and overall. The summary will present the number and percentage of subjects in the Safety Analysis Set. For each column, the denominator for the percentage calculation will be the total number of subjects analyzed for that column.

A summary of subject disposition will be provided. This summary will present the number of subjects screened, enrolled, enrolled but never treated, and the number and percentage of subjects in each of the categories listed below. For the “Treated” category, the denominator for the percentage calculation will be the total number of subjects enrolled. For all other categories, the denominator for the percentage calculation will be the total number of subjects in the Safety Analysis Set.

- Treated (Safety Analysis Set)
- In FAS
- In Intensive PK Analysis Set
- In Population PK Analysis Set
- Completed study treatment
- Did not complete study treatment with reasons for premature discontinuation of study treatment
- Completed the study
- Did not complete the study with reason for premature discontinuation of study

Among subjects who completed the study treatment and who discontinued study treatment, the following number and percentage of subjects will be summarized:

- Subjects who had no HCV posttreatment Week 4 assessment and thereafter (No HCV FU-4 and thereafter)
- Subjects who had HCV posttreatment Week 4 assessment but no HCV posttreatment Week 12 assessment and thereafter (With HCV FU-4 but no FU-12 and thereafter)

If a subject did not have any HCV RNA assessment ≥ 21 days after the last dose of any study drug (ie, lower bound of FU-4 visit for HCV RNA data), the subject is categorized as having “No HCV FU-4 and thereafter”. If a subject had the HCV FU-4 assessment but did not have any

HCV RNA assessment ≥ 70 days after the last dose of any study drug (ie, lower bound of FU-12 visit for HCV RNA data), the subject is categorized as having “With HCV FU-4 but No FU-12 and thereafter”.

In addition, the total number of subjects who were enrolled, and the number of subjects in each of the disposition categories listed above will be displayed in a flowchart.

The following by-subject listings will be provided by subject ID number in ascending order to support the above summary tables:

- Disposition of subjects who complete study treatment and study
- Disposition of subjects who did not complete study treatment and/or study with reasons for premature discontinuation of study drug and/or study
- Lot number and kit ID (if applicable)

4.2. Extent of Exposure

Extent of exposure to study drug will be examined by assessing the total durations of study drug exposure and the level of adherence to the study drug regimen specified in the protocol.

4.2.1. Durations of Exposure to Study Regimen

Total duration of exposure to study drug will be defined as last dose date minus first dose date plus 1, regardless of any temporary interruptions in study drug administration, and will be expressed in weeks using up to 1 decimal place (eg, 4.5 weeks).

The total durations of exposure to study drug will be summarized using descriptive statistics (n, mean, SD, median, Q1, Q3, minimum, and maximum) and using the number (ie, cumulative counts) and percentage of subjects exposed through the following time periods: Baseline (Day 1), Week 1 (Day 7), Week 4 (Day 28), and Week 8 (Day 56) given the fact that only DAA-naïve subjects without cirrhosis have been enrolled in this study. A 3-day window is applied to the last planned on-treatment visit to match with the protocol-specified visit window. Summaries will be provided for the Safety Analysis Set.

4.2.2. Adherence to Study Drug

The level of adherence to the study drug regimen will be assessed based on the total amount of study drug administered relative to the total amount of study drug prescribed.

The adherence will be calculated based on the amount of SOF/VEL/VOX (mg) by the following formula:

$$\text{Level of Adherence(\%)} = \left(\frac{\text{Total Amount of Study Drug Administered}}{\text{Total Amount of Study Drug Prescribed at baseline}} \right) \times 100$$

Where the presumed total amount of study drug (mg) administered to a subject will be determined by the data collected on the drug accountability eCRF using the following formula:

Total Amount of Study Drug (mg) Administered

$$\left(\sum \text{Total Amount of Study Drug (mg) Dispensed} \right) - \left(\sum \text{Total Amount of Study Drug (mg) Returned} \right)$$

Note: If calculated adherence is greater than 100%, the result will be set to 100%.

For adolescent subjects aged 12 to < 18 years receiving the SOF/VEL/VOX 400/100/100 mg once daily, the total amount of drug prescribed for 8 weeks would require 33,600 mg (ie, 400+100+100 mg/day, 56 days).

Subjects who prematurely discontinue study drug for lack of efficacy (ie, virologic failure) will have the total amount of study drug prescribed calculated up to the first date when virologic failure criteria were met. For virologic failure confirmed by 2 consecutive measurements the date of the first measurement will be used. If there are study drug bottles dispensed on or after the subject first met virologic failure criteria, these bottles will not be included in the calculation of adherence. If a bottle is dispensed and the bottle is returned empty, then the number of tablets returned will be entered as zero. If a bottle is dispensed but not returned (missing), the number of tablets taken from that bottle will be counted as zero.

Descriptive statistics for the level of adherence (n, mean, SD, median, Q1, Q3, minimum, and maximum) with the number and percentage of subjects belonging to adherence categories (e.g. < 80%, ≥ 80 to < 90%, ≥ 90%) will be provided for the Safety Analysis Set. No inferential statistics will be provided for duration of exposure and adherence to study drug.

A separate by-subject listing of study drug administration and drug accountability will be provided by subject ID number (in ascending order) and visit (in chronological order).

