3.4. Virologic Response-Based Stopping Criteria

The following on-treatment virologic response-based treatment stopping criteria will be utilized:

- Confirmed HCV RNA \geq LLOQ after 2 consecutive HCV RNA $<$ LLOQ
- Confirmed >1 log₁₀ increase on-treatment nadir

Confirmation should be performed as soon as possible and must occur no later than 2 weeks after an initial observation indicating virologic failure during the on-treatment phase.

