5.1.2. Packaging and Labeling

SOF/VEL/VOX FDC (400/100/100 mg) tablets are packaged in white, high density polyethylene (HDPE) bottles. Each bottle contains 28 tablets, silica gel desiccant, and polyester packing material. Each bottle is enclosed with a white, continuous thread, child-resistant screw cap fitted with an induction-sealed, aluminum-faced liner.

Placebo tablets to assess swallowability of SOF/VEL/VOX FDC (400/100/100 mg) tablets, are packaged in white, high density polyethylene (HDPE) bottles. Each bottle contains 28 tablets, silica gel desiccant, and polyester packing material. Each bottle is enclosed with a white, continuous thread, child-resistant screw cap fitted with an induction-sealed, aluminum-faced liner.

SOF/VEL/VOX FDC (400/100/100 mg) tablet bottles and placebo tablets to be distributed to study centers in the participating countries shall be labeled to meet all applicable requirements of the United States Food and Drug Administration (FDA), and EU Guideline to Good Manufacturing Practice-Annex 13 (Investigational Medicinal Products) and/or local regulations as applicable.

Sufficient quantities of SOF/VEL/VOX FDC (400/100/100 mg) tablets will be shipped to the investigator or qualified designee from Gilead Sciences Clinical Supply Management (or its designee).

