3.4. Examination of Subject Subsets

The efficacy endpoint SVR12 will be analyzed for the following subsets:

- sex (male, female)
- race (black, non-black)
- ethnicity (Hispanic or Latino, non-Hispanic or Latino)
- baseline weight (\leq median, $>$ median)
- IL28B (CC, non-CC [further broken down to CT, TT])

- baseline HCV RNA ($< 800,000$ IU/mL, $\geq 800,000$ IU/mL)
- baseline alanine aminotransferase (ALT) ($\leq 1.5 \times$ ULN, $> 1.5 \times$ ULN)
- prior HCV treatment experience (treatment naïve, treatment experienced - DAA-naïve, DAA experienced)
- number of prior HCV treatments
- most recent response to prior DAA-naïve and DAA HCV treatment (non-response, relapse/breakthrough) for treatment experienced subjects
- study treatment status (completed study treatment, discontinued study treatment)
- adherence to study drug ($< 80\%$, $\geq 80\%$)

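### Two adherence-scoring rules in SAP 4.2.2 can put a subject on the wrong side of 80% in the descriptive SVR12-by-adherence subgroup

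*SAP*

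**What the plan says.** SAP 4.2.2 defines adherence as drug dispensed minus drug returned, divided by the amount prescribed at baseline. For the adolescent 8-week course, "the total amount of drug prescribed for 8 weeks would require 33,600 mg (ie, 400+100+100 mg/day, 56 days". Three further rules shape the score:

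- **Unreturned bottle:** "If a bottle is dispensed but not returned (missing), the number of tablets taken from that bottle will be counted as zero". Nothing reduces the denominator to match.
- **Stopping for virologic failure:** these subjects "will have the total amount of study drug prescribed calculated up to the first date when virologic failure criteria were met". Where failure is confirmed by two measurements, the first date counts. In the numerator, only bottles dispensed on or after that date are dropped.
- **Cap:** "Note: If calculated adherence is greater than 100%, the result will be set to 100" per cent.

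SAP 3.4 lists "adherence to study drug" (below 80%, 80% or more) among the SVR12 subsets. SAP 6.1.3 gives each subset an SVR12 rate, an exact 95% interval and a place on the forest plot. Protocol 5.1.2 says of the tablets, "Each bottle contains 28 tablets". Under Protocol 3.4, confirmation of virologic failure "must occur no later than 2 weeks after an initial observation indicating virologic failure during the on-treatment phase".

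**The concern.** Zero credit for a lost bottle is cautious when the aim is not to overstate exposure. It is not cautious when the same number sorts subjects into adherence groups for an efficacy display, because a missing container then reads as missed doses.

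The virologic-failure rule has a different fault: its two sides cover different periods. Doses taken between the first failing result and the actual stop can make up for doses missed earlier, and the cap removes the ratio above 100% that would have shown the mismatch.

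At stake is the reading of one subgroup. With a planned minimum of 20 adolescents, one or two subjects can be the whole below-80% row. SAP 3.4, 4.2.2 and 6.1.3 give no alternative scoring or sensitivity analysis.

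**Working it through.** **Inputs**
- Daily dose and course: 400+100+100 mg for 56 days (SAP 4.2.2). Only the 8-week group is analysed (SAP 3.2).
- 28 tablets per bottle (Protocol 5.1.2).
- Drug is dispensed on Day 1 (Protocol 6.1.2.1) and at Week 4, when all drug is returned (Protocol 6.3.3). The number of bottles is not stated; two is inferred below.
- Up to 14 days for confirmation (Protocol 3.4).

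**The plan's own figure.** 600 mg × 56 = 33,600 mg, as stated. That is 33,600/600 = 56 tablets, or 56/28 = 2 bottles.

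**Rule 1, lost bottle.** Score = tablets credited / 56.
- All 56 taken, one bottle not returned: 28/56 = 50%.
- Dispensed minus returned, without the special rule: (56 − 0)/56 = 100%.
- If the other bottle came back empty, actual adherence lies somewhere between 28/56 = 50% and 56/56 = 100%. The SAP reports the lower bound.
- Treatment ending on Day 53 (inside the 3-day window) with the first bottle missing: 25/56 = 44.6%.
- If a part-used bottle is lost and replaced, with k tablets already taken from it, an adherent subject scores (56 − k)/56. This is below 80% only when k ≥ 12 (44/56 = 78.6%; k = 11 gives 45/56 = 80.4%).

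**Rule 2, virologic failure.** Score = min(100%, tablets taken from bottles dispensed before the first failing date / days to that date). Take failure first seen on Day 14 and the last dose on Day 28, all from the Day 1 bottle:

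| Tablets taken by Day 28 | Of 28 due | Over 14 (SAP) | Reported |
|---|---|---|---|
| 11 | 39% | 79% | 79% |
| 14 | 50% | 100% | 100% |
| 20 | 71% | 143% | 100% |

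Since 0.8 × 14 = 11.2, such a subject is reported below 80% only after taking 11 or fewer of 28 tablets. The final count does not show when doses were missed. Twenty tablets fits anything from 6/14 (43%) to 14/14 (100%) before failure, and the score is 100% throughout. A subject who took 7 of 14 before failure and 7 of 14 after is 50% adherent on either cutoff, yet scores 14/14 = 100%.

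With confirmation and stopping on Day 21, 14 of 21 (67%) still scores 100%, but 11 of 21 (52%) scores 11/14 = 79%. A failure first seen at the scheduled Week 4 visit is not inflated: the first bottle is returned, the second is excluded, and 14 tablets scores 14/28 = 50%.

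**Effect on the subgroup, assuming 20 subjects**
- *Mix A:* one adherent responder with a lost bottle, one 7-plus-7 virologic failure as above, and 18 adherent responders. Correctly classified: ≥ 80% 19/19, < 80% 0/1. As scored: ≥ 80% 18/19 (94.7%, exact 95% CI 74.0 to 99.9), < 80% 1/1 (CI 2.5 to 100). The order reverses.
- *Mix B:* one adherent non-responder with a lost bottle and 19 adherent responders. Correctly classified: ≥ 80% 19/20, < 80% empty. As scored: ≥ 80% 19/19, < 80% 0/1. A contrast appears where there is none.

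The documents give no bottle-loss rate. For an assumed 1% to 10% per subject, the chance of at least one loss among 20 is 1 − 0.99^20 = 18% to 1 − 0.90^20 = 88%.

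**The case against.** Zero credit is an explicit, prespecified and conservative convention for exposure, and failing to return a bottle may itself signal poor compliance. That stands, and is a reason to keep the rule for the exposure summary and as a worst case. It does not make the score a sound classifier.

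The virologic-failure case is narrow. Failure must be first seen between dispensing visits, in practice at Week 2 or an unscheduled visit, with dosing continued. Protocol 3.4 asks for confirmation as soon as possible, so two weeks is the outer limit. Its first stopping criterion needs two consecutive values below LLOQ, so on scheduled visits only the increase-from-nadir criterion can first be met at Week 2. Protocol 1.3 cites 96% SVR12 in DAA-naive adults without cirrhosis, so such cases should be few. All of this stands.

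A reader might take 71% in the 20-of-28 example as the true adherence. The documents do not support that: the same count fits full adherence before failure, for which the SAP's 100% would be right. For the same reason, simply running both sides to the last dose could blame a failure on doses missed after it.

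The output is also one of twelve descriptive subsets with no statistical comparison (SAP 6.1.2). The accountability listing would expose unreturned bottles, and sparse PK samples give separate evidence of dosing. These limit the harm but do not correct the forest plot.

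**Conclusion.** The concern holds in a limited form and is minor. Both rules, as written, can put a subject on the wrong side of 80%. Rule 1 gives a fully adherent 8-week subject at most 50%, assuming two 28-tablet bottles and no replacement. Rule 2 can report 100% for a subject who took half the doses, provided failure is first seen between dispensing visits and dosing continues to confirmation.

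A reader might infer that the rules will systematically shrink or reverse the adherence-response contrast. The documents do not support that. Mix A reverses it and Mix B creates one; the direction depends on which subjects lose bottles or fail early, and no rates are given. Nor does the point reach the main results: the effect is confined to the descriptive subgroup and the adherence summary, and the primary PK endpoint and overall SVR12 do not use the score.

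**What to change.** In SAP 4.2.2 and 3.4:

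1. **Virologic-failure discontinuations:** use one cutoff date in numerator and denominator. Take the first-failure date where a tablet count at that date exists; otherwise take the actual last dose date for both sides and flag the value as including post-failure dosing. The fallback is needed because Protocol 6.3.2 lists no drug return at Week 2.
2. **Unreturned bottles:** show these subjects as not evaluable in the SVR12-by-adherence subgroup and give their number. Keep the zero-tablet rule in the exposure summary and as a labelled worst-case line beside the subgroup.

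The cost is a change of SAP wording and a small amount of programming, with no new data: last dose date and accountability amounts are already defined or collected. The downside is that a few subjects become not evaluable in one subgroup, possibly selectively, which is why the worst-case line stays.
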